 - **Outcomes/measures:** At least 90% of all outcomes planned for the RCT in Aim 3 (STTR Phase II) will be measured in the 8 patients: 1) actigraphy counts, 2) RASS sedation/agitation score,¹ 3) CAM-ICU delirium score,¹ 4) medication use, 5) satisfaction/acceptability/perceptions of novel restraint. Incidence of self-extubation will also be reported in addition to the following measures of efficacy: 1) patient-reported satisfaction measures including comfortable, safe, effective, preferable and more humane; and 2) staff-reported satisfaction measures including easy to don/doff, easy to change level, safe for staff, effective, preferable and more humane. See Aim 3 for these RCT measures.

- **Data collection/management, quality assurance & analysis:** See Aim 3.
- **Sample size:** N=8 was based on feasible enrollment from the single study site during the 9-month Phase I period (i.e., ~1 patient/month). Literature suggests that there is no advantage to including more than 6-10 subjects per group in a Phase I study, and most chemotherapeutic phase I studies have N=3 per cohort.¹ Thus, N=8 is adequate for the proposed Aims to prepare for the RCT in Aim 3.
- **Phase I Study follow-up.** The engineer will prepare a report on the outcomes of all assessments based upon STTR Phase I, and will decide (in consultation with the project leadership team) which device improvements/modifications will be required before use of device in Aim 3 (STTR Phase II).

PHASE II (3-site RCT to compare the novel restraint to traditional wrist restraints)

[figure not shown]
Aim 3: To conduct a multi-site, within-patient randomized crossover trial in older critically ill mechanically ventilated patients who require restraint, to compare the *Exersides™* restraint vs. traditional wrist restraints.

Overview and Study Design Phase II. The objective of the Phase II project is to conduct an RCT to measure 3 outcomes:

1. Mobility/activity evaluated by actigraphy (primary outcome)
2. Agitation, delirium, medication use (sedative, analgesic, and antipsychotic), and incidence of self-extubation (secondary outcomes)
3. Satisfaction with, and acceptability/perceptions of, the device by patient, family, and clinicians (secondary outcomes)

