Potential risks from the *Exersides*TM restraint device are very low. Our own preliminary data demonstrate safety in that no adverse or severe adverse events (i.e. no self-removal of endotracheal tubes, feeding tubes, intravenous lines, etc.) – these preliminary data are from a pilot study that has already taken place that enrolled critically ill patients in a single intensive care unit. Although self-removal of tubes and lines is a risk, as occurs with any existing currently available restraint device, we anticipate that this risk is very low due to the design of the *Exersides*TM restraint that intentionally was created to further reduce this risk in comparison to traditional restraints. Other potential risks include skin breakdown from the *Exersides*TM restraint device, and a theoretical increased risk of increased removal of upper extremity peripheral IVs, but we did not observe any of these events in our pilot study.

There are few alternative treatments to participating in this RCT. Use of the *Exersides*TM restraint device is not standard of ICU care at any clinical center. However, this study will not alter clinical care that occurs with regard to other aspects of critical illness. Specifically, only patients whose physicians have already written an order requiring physical restraints will be considered for the study. The novel *Exersides*TM restraint device will only be used while such an order is active, as part of routine clinical care (i.e. no patient will receive the *Exersides*TM restraint device without a need for physical restraint as documented/ordered by the ICU clinicians). All study sites currently follow (and will continue to follow throughout the duration of the study) Joint Commission requirements for re-assessment and re-ordering restraints at least once every 24 hours. If a restraint is no longer required/ordered as part of routine clinical care, then use of the *Exersides*TM restraint device will immediately stop and not re-start unless a renewal of a restraint order is done, as required by clinical circumstances. In no way will the study have any influence over the ordering of restraints as part of clinical care in the ICU.

ADEQUACY OF PROTECTION AGAINST RISKS

Recruitment and Informed Consent

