The novel restraint device being tested in the FREEDOM Trial is considered so low-risk that it is exempt

from FDA IDE regulations. Nevertheless, participants will be monitored for medical events of interest including skin laceration, upper extremity joint pain, and equipment damage that may not be serious but may be related to the novel restraint intervention. These data will be collected daily while the subject is on study (through day 3 for the pilot study and day 7 for the RCT). These data will be recorded in the electronic database.

2. *Adverse Event (AE) Reporting*

Given the high acuity of diseases and morbidity related to critical illness in the patient population under study (over age 60 years old receiving invasive or non-invasive mechanical ventilation and requiring restraint), it is difficult to identify an adverse event (AE) within the constellation of symptoms related to the normal evolution of critical illness. Therefore, expected AEs (e.g. abnormal laboratory values, aberrant physiology such as fever or tachycardia or hypotension, etc.) consistent with the underlying pathophysiology or progression of underlying illness will neither be collected nor reported. Only AEs that are both unexpected and felt to be related (to any degree) to the novel restraint device will be collected and reported, the majority of which will be considered “events of interest” as above. The investigator will use his/her judgment to determine whether an AE is considered to be definitely related, probably related, possibly related, unlikely related, or not related (see table below in 5.a.). These unexpected and related (to any degree) AEs will be documented in the participant medical record and/or study file. It is the responsibility of the investigator to review all documentation (e.g. hospital progress notes, laboratory results, diagnostic reports, etc.) regarding each event. This reporting process is outlined below.

3. *Serious Adverse Event (SAE) Reporting*

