Similar to AEs, given the high acuity of diseases and morbidity related to critical illness in the patient population under study (over age 65 years old receiving invasive or non-invasive mechanical ventilation and requiring restraint), it is difficult to identify an SAE within the constellation of symptoms related to the normal evolution of critical illness. Only ‘unexpected’ SAEs (inconsistent with underlying pathophysiology or progression of underlying disease) will be collected and reported. Expected SAEs will not be reported (see description below). The investigator will use his/her judgment in determining whether an event is considered to be reportable per guidelines. SAEs will be documented in the participant medical record and/or study file. It is the responsibility of the investigator to review all documentation (e.g. hospital progress notes, laboratory results, diagnostic reports, etc.) regarding each event. This reporting process is outlined below.

3.A. DEFINITION OF SERIOUS ADVERSE EVENTS (SAEs)

An event will be considered an SAE if it meets any one or more of the following criteria:

- A. Results in death
- B. Is life-threatening - an event where a participant is at risk of death at the time of the event. It does not refer to an event that hypothetically might have caused death if it was more severe.
- C. Prolongation of hospitalization - any substantial extension of an inpatient hospitalization beyond the stay anticipated/required in relation to participant's condition prior to the SAE, as determined by the investigator or treating physician.
- D. Results in Disability or Incapacity - is defined as a substantial disruption of a person's ability to conduct normal life functions.
- E. Led to fetal distress, fetal death or a congenital abnormality or birth defect
- F. Important medical event - are those that may not be immediately life-threatening, but may jeopardize the participant and may require intervention to prevent one of the other serious outcomes listed above.

3.B. EXPECTED SAEs

As the patient population under study are hospitalized and critically ill at baseline, care must be taken to determine if an event is outside of what would be expected given the degree and nature of the critical

illness prior to the serious adverse event. In the population under study, some examples of potential expected SAEs include:

- Abnormalities in oxygenation and/or ventilation expected for the degree of injuries sustained.

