- Fluctuations in hemodynamic measures expected for the degree of injuries sustained.
- Agitation and/or pain responses expected for the degree of injuries sustained.
- Complications directly related to sustained injuries.
- Use of medications, blood products, support devices and other therapies expected for the degree of injuries sustained.

3.c. *Expected Deaths*

Importantly, as approximately 15-25% of participants will die from their critical illness, we anticipate that deaths in this study will be expected and occur as a result of the patients' underlying illness, with associated mortality data recorded in the CRF. Please note that reporting an expected death as an SAE via the electronic database report form is not required. However, it is left to each individual site to determine whether it meets local requirements for reporting to the IRB. Unexpected deaths should be reported as described below.

3.D. UNEXPECTED SAEs

All unexpected SAEs must be reported to the PIs and Project Manager using the appropriate form as outlined below.

3.e. Definition of Unexpected SAE

Any SAE occurring in a subject participating in this Trial where the nature, severity, or frequency of the event is not consistent with the expected natural progression of any underlying disease, disorder, or condition of the subject(s) experiencing the adverse event and the subject's predisposing risk factor profile for the adverse event (e.g. sudden death from MI in a person with ARDS and sepsis without known heart disease).

4. Reporting Period

Participants should be monitored for related AEs (to any degree) and unexpected SAEs from the time of randomization until the day after the on-study period is complete (study day 7 for multi-site RCT as participants will be on study for maximum of 6 days, or 24 hours after removal of restraint device under study, whichever is earlier).

5. Reporting Timelines

Related AEs (to any degree – definitely, probably, possibly, or unlikely) and unexpected SAEs should be reported to the PIs and Project Manager ([name], [name], and [name]) within 24h of knowledge of the occurrence of the event. The site is expected to notify the PIs or Project Manager by phone or email and complete the Related AE and Unexpected SAE report form to submit the initial report, as well as any follow-up reports.

5.a. Initial Report

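### Non-serious harms in the RCT are collected by attribution to the novel device, and self-extubation has no table row, schedule or analysis, so a between-device description of restraint harms is not assured

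*Combined protocol and SAP*

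**What the plan says.** The combined protocol and SAP deals with RCT harms in several places.

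- **Non-serious AEs** (Adverse Event (AE) Reporting, item 2): "Only AEs that are both unexpected and felt to be related (to any degree) to the novel restraint device will be collected and reported". Reporting Timelines, item 5, shows how far relatedness stretches: "definitely, probably, possibly, or unlikely) and unexpected SAEs should be reported to the PIs and Project Manager".
- **Events of interest** (item 1): "participants will be monitored for medical events of interest including skin laceration, upper extremity joint pain, and equipment damage". They are recorded daily, through day 7 in the RCT. The same sentence describes them as events that "may be related to the novel restraint intervention".
- **Serious events** (item 3): only unexpected "SAEs (inconsistent with underlying pathophysiology or progression of underlying disease) will be collected and reported". No link to the device is required.
- **Deaths** (Expected Deaths): mortality is recorded in the CRF.
- **Self-extubation** (Overview and Study Design Phase II): the second group of outcomes ends with "and incidence of self-extubation (secondary outcomes".
- **Acknowledged risk** (Potential Risks): self-removal of tubes and lines is a risk with any restraint. The design is said to lower it relative to traditional restraints, yet the section also concedes "a theoretical increased risk of increased removal of upper extremity peripheral IVs".
- **Blinding**: patients, families and ICU clinicians cannot be blinded. The blinded assessor covers actigraphy only.

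**The concern.** The device is meant to allow more arm movement, and the primary outcome rewards movement. The natural counterweight is loss of tubes and lines, self-removal of the restraint, and injury to skin or staff. The plan makes a comparative statement about these risks, so a reader will expect the trial to describe them under both devices.

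The AE rule works against that. An event enters only if an unblinded investigator links it to one of the two devices. Two identical events can therefore be counted differently according to what the patient was wearing. The direction of the resulting bias is not fixed. One-sided capture can make the novel device look worse, while reluctance to attribute can make it look better. Self-extubation, the most serious of these harms, is promised as an outcome but given no means of measurement or analysis.

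**Working it through.** The plan states no harm rate and no safety precision, so there is no figure to reproduce. The check is a comparison of sections, followed by arithmetic for scale.

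**1. Route of a non-serious event.** Take a dislodged peripheral IV. Under the novel device it qualifies if it is unexpected and related to any degree, with unlikely counting as related. Under wrist restraint the investigator must judge its relation to a device the patient is not wearing. On Days 1 and 2, when both are worn on the same day, it might be graded unlikely and kept. On Days 3 to 6, in a patient assigned to wrist restraint, not related is the natural grade and the event is lost. The causality table in Initial Report adds uncertainty, because it grades relation to study participation, not to the novel device.

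**2. Named harms at each stage.**

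| Harm | Pilot | Phase I | RCT |
|---|---|---|---|
| Self-extubation | yes | reported measure | named in the overview only |
| Feeding tube or IV removal | yes | not among the seven criteria | not named |
| Self-removal of restraint | yes | criterion 5 | not named |
| Laceration | as skin breakdown | criterion 1 | event of interest |
| Pressure ulcer | as skin breakdown | criterion 2 | not named |
| Patient injury | yes | criterion 3 | not named |
| Clinician injury | yes | criterion 4 | not named |
| Bed or equipment damage | no | criteria 6 and 7 | equipment damage is an event of interest |
| Arm joint pain | no | no | event of interest |

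**3. Self-extubation after the overview.** Table 7 has secondary rows for medication, agitation, delirium, satisfaction and perceptions. The Outcome 2 text and the SAP's listed secondary endpoints cover agitation, delirium and medication. None of these mentions self-extubation, nor do the events of interest. The SAP contains no between-device safety analysis.

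**4. Maximum exposure.** This assumes 54 patients, 27 per group, and no early end to restraint.
- Days 1 and 2, daytime sessions: 2 sessions x 4 h = 8 h per device per patient; 54 x 8 = 432 h for each device.
- Nights after Days 1 and 2, all in wrist restraint: 5pm to 9am = 16 h; 54 x 2 x 16 = 1,728 h.
- Wrist restraint up to the morning of Day 3: 432 + 1,728 = 2,160 h, which is 2,160 / 432 = 5 times the novel-device hours.
- Days 3 to 6: 4 x 24 = 96 h if worn round the clock; 27 x 96 = 2,592 h per group.

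**5. Precision with no events** (exact two-sided 95% upper limit).
- Per patient, 1 - 0.025^(1/n): n = 54 gives 6.6%; n = 27 gives 12.8%.
- Per device-hour, -ln(0.025)/T = 3.689/T: 3.689/432 = 0.85 per 100 h; 3.689/2,592 = 0.14 per 100 h.

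**6. Power for scale, 27 v 27.** The rates are assumed and are not in the documents.

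| Rates | Normal approximation | Fisher's exact test | Per arm for 80% power (normal approximation) |
|---|---|---|---|
| 2% v 5% | 9% | 0.1% | 588 |
| 5% v 10% | 10% | 1.3% | 435 |
| 5% v 15% | 23% | 7.0% | 141 |

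At such small counts the exact figures are the safer guide.

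**The case against.** A reader might infer that the trial has no comparator for any of its key harms, or that harms under wrist restraint are never recorded. The documents do not support that. Unexpected serious events need no link to the device, and a self-extubation could qualify as an important medical event. Events of interest are monitored daily in participants generally, from an open list, and collection is not confined to periods on the novel device. Deaths go into the CRF. Laceration and equipment damage do carry over from Phase I.

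Nor do the documents show a decision to leave self-extubation out. It is named as an outcome of a comparative trial, the SAP's list of secondary endpoints is introduced with a non-exhaustive verb, and its logistic model for binary endpoints could in form accommodate it. Patients are observed and video-recorded in the Day 1 and 2 sessions. The DSMB reviews safety after 27 patients and may ask for more data. Comparative safety is not a Phase II hypothesis, and the sample size was set for actigraphy.

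All of this stands, and it limits the point, but it does not close the gap. Line removal, device self-removal and minor skin injury need not be serious. Whether a self-extubation counts as unexpected is left to judgement, and agitation responses appear among the examples of expected serious events. The events of interest are described by possible relation to the novel device, and item 2 says most AEs passing its filter will be events of interest. A model with no defined endpoint or schedule behind it does not guarantee data.

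**Conclusion.** The concern holds in a limited form. Non-serious AE capture depends on open-label attribution to one device. Self-extubation is an internal inconsistency: named once and never operationalised. Tube or line removal, device self-removal, pressure injury, and patient or clinician injury are not named RCT events. A between-device description of restraint harms is therefore not assured, although parts of one may be recoverable from the other streams.

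This rests on the text and on no assumed rate. It should be corrected, but it does not threaten the primary analysis. Two further inferences should be avoided. Exposure to the two devices is equal only in the Day 1 and 2 daytime sessions, because everyone returns to wrist restraint overnight as ordered. And symmetric collection would not let 54 patients show equivalent safety: upper limits of 6.6% (0 of 54) and 12.8% (0 of 27), and the low power at the assumed rates, allow description only.

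**What to change.** - Record one fixed list for every patient under both devices, regardless of attribution: self-extubation, feeding tube or line removal, self-removal of restraint, skin or pressure injury, arm joint pain, patient or staff injury, and equipment damage. Note the time and the device worn.
- Count overnight wear as wrist-restraint exposure, but show it apart from the daytime sessions. It has no novel-device counterpart, and no sensor or video data are recorded overnight when study staff are unavailable.
- Add self-extubation to Table 7 and to the SAP, with a definition and a recording schedule.
- Report events per device-hour with exact intervals, by device on Days 1 and 2 and by randomised group on Days 3 to 6. State that no claim of equivalent safety will be made.
- Keep causality grading as a separate field, and reconcile relatedness to the novel device (item 2) with relatedness to study participation (causality table).

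The cost is a short checklist added to the existing daily collection, some SAP wording, and a few more non-serious events to log. The intervals will be wide.

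### Section 2 collects a device-related AE only if it is also unexpected, while sections 4 and 5 require every related AE, so the rules conflict for device-related events that resemble the underlying illness

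*Combined protocol and SAP*

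**What the plan says.** All of this is in the Combined protocol and SAP, mostly in the part on adverse event and unanticipated problem reporting.

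- **Section 2 (Adverse Event Reporting), exemption.** Expected AEs "consistent with the underlying pathophysiology or progression of underlying illness will neither be collected nor reported". No exception is made for events attributed to the device.
- **Section 2, collection.** "Only AEs that are both unexpected and felt to be related (to any degree) to the novel restraint device will be collected and reported". The sentence goes on to say that most of these will count as events of interest.
- **Section 2, documentation.** "These unexpected and related (to any degree) AEs will be documented in the participant medical record and/or study file".
- **Section 4 (Reporting Period).** "Participants should be monitored for related AEs (to any degree) and unexpected SAEs from the time of randomization".
- **Section 5 (Reporting Timelines).** "Related AEs (to any degree – definitely, probably, possibly, or unlikely) and unexpected SAEs should be reported to the PIs and Project Manager", with the limit "within 24h of knowledge of the occurrence of the event". The site must also "complete the Related AE and Unexpected SAE report form".
- **Section 1 (Events of Interest).** A separate daily capture in the electronic database, running to day 7 in the RCT. It names skin laceration, joint pain in the arm and damage to equipment, and applies no test of expectedness.
- **Potential Risks.** The device risks named are self-removal of tubes and lines, skin breakdown, and "a theoretical increased risk of increased removal of upper extremity peripheral IVs".

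**The concern.** Section 2 applies two tests to a non-serious AE (unexpected and related). Sections 4 and 5 apply one (related). Under section 2, an investigator who believes the device caused an event still does not collect it as an AE if it is also consistent with critical illness. Under section 5 the same event has to be reported within 24 hours.

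The RCT runs at three sites. If one site works from section 2 and another from section 5 and the form, their AE counts are not comparable and the pooled count has no clear definition. The class in dispute also matters for this device. Skin breakdown and loss of a peripheral IV could each be put down to being old, ventilated and restrained, and each is a risk the protocol attributes to the device.

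**Working it through.** No arithmetic applies: the point does not depend on sample size, power or an event rate. The check is to put the two rules side by side for each kind of non-serious AE.

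| Non-serious AE | Section 2 | Sections 4 and 5 | Agree? |
|---|---|---|---|
| Unexpected, related | collected and reported | reported within 24 hours | yes |
| Expected, related | not collected | reported within 24 hours | **no** |
| Unexpected, not related | not collected | not reported | yes |
| Expected, not related | not collected | not reported | yes |

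The conflict is confined to one cell of four. Section 5 widens that cell by counting a rating of unlikely as related.

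**Does any text reconcile the rules?** None was found. No sentence defines a related AE as one that is also unexpected, and none gives one section precedence. Section 4, section 5 and the form's name all attach unexpectedness to SAEs alone.

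**Are events in the disputed cell captured elsewhere?** Partly.

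- Laceration, joint pain and equipment damage: yes, daily, as events of interest.
- Agitation and self-extubation: yes, as secondary outcomes (Phase II overview; RASS timing in Table 7), but without an assessment of device causality.
- Skin breakdown and peripheral IV removal: not named as events of interest and not listed as RCT outcomes. The list in section 1 is open-ended, so a site could add them, but nothing requires it.
- Illness-like physiology, such as the tachycardia that section 2 gives as an example of an expected AE: no AE or event-of-interest record under section 2, even if rated device-related.

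**How were the two named risks handled before the RCT?** The earlier pilot counted both IV dislodgement and skin breakdown in its definition of an adverse event (Preliminary Studies, item 3). Phase I made pressure ulcer of Stage 3 or greater a safety criterion (Aim 2, Phase I Outcomes). The RCT text has no equivalent list.

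**The case against.** The strongest reply is that sections 4 and 5 are shorthand. Section 2 decides what is collected and closes by pointing to the process described below it. Sections 4 and 5 then supply only the period and the deadline for that set. The literal reading also has an odd result: a related but expected non-serious AE would be reported within 24 hours, while section 3 leaves a related but expected SAE unreported. This makes shorthand plausible. It does not settle the matter, because section 5 spells out its own term in a parenthesis, by grade of relatedness and with no test of expectedness, and in the same sentence states that test for SAEs. Staff working from section 5 and the form have no cue to apply a second filter.

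It is also fair to say that section 2's own examples of expected AEs are laboratory abnormalities, fever, tachycardia and hypotension. That skin breakdown or IV loss would be classed with them is a possibility, not something the text states.

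Three stronger readings are not supported:

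- A reader might infer that these events are never recorded. That is true only of AE collection under section 2. The daily events of interest and the outcome assessments capture some of them.
- A reader might infer that expedited reporting to the DSMB and NIA is affected. Section 5.c covers unexpected, related SAEs only, so this mismatch does not touch it. The DSMB must also approve the plan for identifying and transmitting AE information before the RCT starts, which is a chance to resolve the conflict, though not a resolution.
- A reader might want a count of lost reports. The documents give no rate of related but expected AEs, and any figure would only restate the assumption behind it.

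**Conclusion.** The conflict is real and stands in the current text. Two stated rules give different AE data for non-serious events that are device-related but consistent with the underlying illness, and nothing says which applies. It affects site-level collection and the 24-hour report to the principal investigators and Project Manager. It does not affect the primary actigraphy analysis.

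Its size cannot be put in numbers from the documents. In scope it is one class of event, partly covered by other data streams. The practical gap is clearest for skin breakdown and peripheral IV removal, and that rests on one assumption: that some investigators would judge such events expected in this population. The contradiction between the sections does not need that assumption. The change should be made, because the data at issue are safety data on a novel device and the remedy is short.

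**What to change.** Bring sections 2, 4 and 5 and the report form to one AE collection rule, applied at all three sites.

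1. **Simplest alignment.** In section 2, drop the unexpectedness condition for device-related AEs in both places where it appears: the collection sentence and the later documentation sentence. Changing only the first would leave section 2 contradicting itself. Limit the exemption from collection and reporting to AEs judged not related to the device.
2. **Alternative.** If the sponsor keeps the narrower rule, sections 4 and 5 and the name of the form must state that AEs have to be unexpected as well as related.
3. **In either case.** Add skin breakdown or pressure injury, and peripheral IV removal, to the daily events of interest, recorded whether or not they are expected.

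Cost: a few sentences of text and a change to the daily form. The first option also brings more causality ratings and AE forms. Section 2 now exempts common abnormalities of physiology and laboratory values outright; these would need a relatedness judgement, and those rated unlikely would count as related. The reported AE count for the novel device would rise slightly. The second option avoids that extra work but leaves related, illness-like AEs outside the AE record, apart from those captured as events of interest.
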